9.7.1.7 Pharmacokinetic, Pharmacodynamic, Pharmacogenomic, and Other Biomarker Analyses

9.7.1.7.1 PHARMACOKINETIC ANALYSIS

Lenvatinib and everolimus concentration versus time data will be tabulated and summarized and graphically presented.

Plasma concentrations of lenvatinib from the intense sampling in Phase 1 will be used to determine the following PK parameters: area under the plasma concentration time course profile (AUC), maximum observed concentration (C_{max}), and time from dosing to the maximum observed concentration (T_{max}). Other PK parameters may be determined as data permit.

For both lenvatinib and everolimus, data from Phase 1 and 2 of the study will be pooled with available data from other studies and subjected to population PK analysis. For each drug, the PK model will be parameterized in terms of clearance and volume of distribution.

Details of the population PK analysis will be provided in a separate analysis plan.

9.7.1.7.2 PHARMACODYNAMIC, PHARMACOKINETIC/PHARMACODYNAMIC, PHARMACOGENOMIC, AND OTHER BIOMARKER ANALYSES

Correlation between clinical response to treatment associated with a combination of lenvatinib and everolimus and blood or tumor biomarkers will be examined using descriptive statistics and graphic displays as appropriate. Details will be provided in a separate analysis plan.

Pharmacokinetic/PD exposure-safety relationships will be explored. Safety endpoints will be most frequent AEs of special interest and dose reductions. Exploratory/graphical analyses will be conducted for PK/PD evaluations, and may be followed by model-based analyses. A detailed analysis plan will be provided separately.

9.7.1.8 Safety Analyses

Safety variables include study drug exposure, treatment-emergent adverse events (TEAEs), laboratory tests, vital signs, 12-lead ECGs, cardiac function by echocardiography/MUGA scan, urine dipstick, and Lansky play scores or Karnofsky performance scores.

All toxicities will be summarized. The following are evaluability criteria for toxicity analysis:

- **Evaluable for toxicity:** All subjects who received at least one dose of study treatment are evaluable for toxicity. For Phase 1, toxicities during Cycle 1 will be used for the purpose of dose escalations according to the rolling 6 design. Subjects who developed a DLT or received at least 75% of the prescribed dose during cycle 1 are considered fully evaluable for toxicity for the purpose of dose escalation.

The incidence of treatment-emergent adverse events (TEAEs) and SAEs will be summarized by system organ class and preferred term. Laboratory test data, vital signs, 12-lead ECGs, cardiac function by echocardiography/MUGA scan, urine dipstick, Lansky play scores or Karnofsky performance scores, and their changes or shifts from baseline will be summarized using descriptive statistics, as appropriate. Summary of study drug exposure will be provided. Prior and concomitant medications, medical/surgical history and subject demographics will be summarized.

9.7.1.8.1 EXTENT OF EXPOSURE

The number of cycles/days on treatment, quantity of study drug administered, and the number of subjects requiring dose reductions, treatment interruption, and treatment discontinuation due to AEs will be summarized.

9.7.1.8.2 ADVERSE EVENTS

The AE verbatim descriptions (investigator terms from the CRF) will be classified into standardized medical terminology using the Medical Dictionary for Regulatory Activities (MedDRA). Adverse events will be coded to the MedDRA lower level term (LLT) closest to the verbatim term. The linked MedDRA preferred term (PT) and primary system organ class (SOC) are also captured in the database.

A TEAE is defined as an AE that emerges during treatment, having been absent at pretreatment (baseline) or

- Reemerges during treatment, having been present at pretreatment (baseline) but stopped before treatment, or
- Worsens in severity during treatment relative to the pretreatment state, when the AE is continuous.

Only those AEs that are treatment emergent will be included in summary tables. All AEs, treatment emergent or otherwise, will be presented in subject data listings.

The incidence of TEAEs will be reported as the number (percentage) of subjects with TEAEs by SOC and PT. A subject will be counted only once within an SOC and PT, even if the subject experienced more than 1 TEAE within a specific SOC and PT. The number (percentage) of subjects with TEAEs will also be summarized by CTCAE grade if appropriate.

The number (percentage) of subjects with treatment-related TEAEs will be summarized by SOC and PT. Treatment-related TEAEs include those events considered by the investigator to be related to study treatment.

The number (percentage) of subjects with treatment-emergent SAEs will be summarized by MedDRA SOC and PT. A subject data listing of all SAEs will be provided.

The number (percentage) of subjects with TEAEs leading to discontinuation from study drug or leading to study drug dose changes will be summarized by MedDRA SOC and PT. A

subject data listing of all AEs leading to discontinuation from study drug or leading to study drug dose changes will be provided.

9.7.1.8.3 LABORATORY VALUES

Laboratory results will be summarized using Système International (SI) units, as appropriate. For all quantitative parameters listed in Section 9.5.1.5.3, the actual value and the change from baseline to each post-baseline visit will be summarized by visit using descriptive statistics. Qualitative parameters listed in Section 9.5.1.5.3 will be summarized using frequencies (number and percentage of subjects), and shifts from baseline to worst postbaseline will be reported using shift tables. Percentages will be based on the number of subjects with both nonmissing baseline and at least 1 post-baseline results.

Laboratory parameters will be categorized according to CTCAE grades, and shift tables from baseline CTCAE grades to the worst post-baseline grades will be provided.

9.7.1.8.4 VITAL SIGNS

Descriptive statistics for vital signs parameters (ie, systolic and diastolic BP, pulse, respiratory rate, temperature, weight) and changes from baseline will be presented by visit. A shift table of hypertension from baseline to worst post-baseline grades will be provided.

9.7.1.8.5 ELECTROCARDIOGRAMS

Descriptive statistics for ECG parameters and changes from baseline will be presented by visit. Shift tables will present shifts from baseline in ECG interpretation (categorized as normal, abnormal, not clinically significant, and abnormal clinically significant) to the worst post-baseline assessment.

9.7.1.8.6 OTHER SAFETY ANALYSES

Shift tables of Lansky play scores and Karnofsky performance scores from baseline will be provided.

Descriptive statistics and changes from baseline for left ventricular shortening fraction assessed on echocardiogram and LVEF assessed on echocardiogram or MUGA scans will be presented. Percent reduction from baseline will also be summarized.

9.7.2 Determination of Sample Size

Phase 1 – Determination of the Maximum Tolerated Dose: The total number of subjects required for the Phase 1 portion of this study will depend upon the toxicities observed as the study progresses. The minimum number of evaluable subjects required for this study is 4. The projected maximum number of evaluable subjects required is 48. Once the MTD or RP2D has been defined, up to 6 additional subjects with recurrent or refractory solid tumors may be enrolled to acquire PK data in a representative number of young subjects. Therefore, a maximum of 54 subjects are expected to be enrolled in the 4 dose escalation levels, and PK expansion. The Phase 1 part of the study is expected to be completed within 18 months. In

the event that each of Dose Levels -1, 1, 2, and 3 are expanded to 12 subjects, an absolute maximum of 54 subjects would be required allowing for 20% to be non-evaluable and including up to 6 additional subjects for PK analysis.

Phase 2: Phase 2 will require a minimum of 10 evaluable subjects per disease cohort and a maximum of 20 (10 evaluable subjects in each stage of Simon's optimal 2-stage design). Therefore, a maximum of 22 subjects per cohort will be enrolled to allow for a 10% non-evaluable rate. This design has 88% power to detect a 20% increase in the response rate at the significance level of one-sided $\alpha = 0.07$ assuming a null response rate of 5% and alternative response rate $\geq 25\%$.

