- Phase 1: 4 to 48 evaluable subjects. In the event that each of the 4 dose levels (-1, 1, 2, and 3) are expanded to 12 subjects and 6 additional subjects need to be enrolled in the PK Cohort, a maximum of 54 subjects (allowing for 20% to be non-evaluable and including the additional 6 subjects for PK analysis) will be enrolled.
- Phase 2 Cohorts 1 - 3: 10 to 20 evaluable subjects per cohort (maximum 22 subjects enrolled per cohort allowing for 10% to be non-evaluable). A maximum of 66 subjects will be enrolled in Phase 2. In each cohort, at least 50% of the subjects enrolled will be <18 years old at the time of informed consent.

Inclusion Criteria

1. Histologically or cytologically confirmed diagnosis of the following tumor types:
 - a. Phase 1: Recurrent or refractory solid tumors (excluding hepatoblastoma and lymphomas), including primary central nervous system (CNS) tumors; subjects must have either measurable or evaluable disease. Subjects with diffuse intrinsic pontine glioma, optic pathway glioma, or pineal tumors with elevated tumor markers (alpha-fetoprotein [AFP] and beta-human chorionic gonadotropin [β -hCG] [or hCG]) do not require histological or cytological confirmation of diagnosis.
 - b. Phase 2: Recurrent or refractory tumors; subjects must have measurable disease
 - Cohort 1: Ewing sarcoma/pPNET
 - Cohort 2: Rhabdomyosarcoma
 - Cohort 3: HGG (subjects with Diffuse Intrinsic Pontine Glioma are not eligible)
2. Measurable disease that meets the following criteria (Phase 2):
 - a. Response Evaluation Criteria in Solid Tumors (RECIST) 1.1 (for all tumor types except HGG)
 - At least 1 lesion of ≥ 1.0 cm in the longest diameter for a non lymph node or ≥ 1.5 cm in the short-axis diameter for a lymph node which is serially measurable according to RECIST 1.1 using computed tomography /magnetic resonance imaging (CT/MRI).
 - b. Response Assessment in Neuro-Oncology (RANO) for HGG (Wen, et al., 2010)
 - At least one lesion must be measurable as defined as a bi-dimensionally contrast-enhancing lesion with clearly defined margins by CT or MRI scan, with a minimal diameter of 1 cm, and visible on 2 axial slices which are preferably at most 5 mm apart with 0 mm skip.

Lesions that have had external beam radiotherapy (EBRT) or locoregional therapies such as radiofrequency (RF) ablation must show evidence of progressive disease based on RECIST 1.1 to be deemed a target lesion.

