6	≥2	0, 1, 2, 3 or 4	0, 1, 2, 3 or 4	De-escalate*

DLT = dose-limiting toxicity

* If 6 subjects already entered at next lower dose level, the maximum tolerated dose (MTD) has been defined.

**If final dose level has been reached, the recommended dose has been reached.

If 2 or more of a cohort of up to 6 subjects experience DLT at a given dose level, then the MTD has been exceeded and dose escalation will be stopped. In the event that 2 DLTs observed out of 6 evaluable subjects are of different classes of Adverse Effects (eg, hepatotoxicity and myelosuppression), expansion of the cohort to 12 subjects will be considered (if one of the DLTs does not appear to be dose-related, the Adverse Effects are readily reversible, **AND** Protocol Steering Committee (PSC) **AND** sponsor all agree that expansion of the cohort is acceptable). Subjects who on PSC review are not deemed to be evaluable for DLT assessment may be replaced.

All subjects in the Phase 1 Dose Escalation phase will have samples taken for PK analysis with the intent at the end of Phase 1 of having evaluable PK data from minimally 6 subjects aged 2 to <6 years old, 6 subjects ≥ 6 to <12 years old, and 6 subjects ≥ 12 years old. Once the MTD or RP2D has been defined, 0 to 6 additional subjects will be enrolled to attain the goal of having evaluable PK data from minimally 6 subjects aged 2 to <6 years old, 6 subjects ≥ 6 to <12 years old, and 6 subjects ≥ 12 years old.

Protocol Steering Committee

The sponsor will closely evaluate the risks and benefits of the study throughout its conduct, along with the PSC as needed. The PSC may review available relevant data: DLT and safety data including laboratory assessments, 12-lead electrocardiograms (ECGs), dose administration, etc.

Toxicity Monitoring

The DLT observation period for the purposes of dose-escalation will be the first cycle of therapy. Routine Phase 1 monitoring for clinical and laboratory toxicities will be used. Blood pressure (BP) monitoring will occur at least weekly during the first 2 cycles.

Dose-Limiting Toxicity

Dose-limiting toxicity will be assessed according to Common Terminology Criteria for Adverse Events (CTCAE) v4.03 and is defined as any of the following events that are possibly, probably, or definitely attributable to lenvatinib or everolimus. Dose-limiting hematological and non-hematological toxicities are defined differently.

A. Non-hematological DLT:

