9.3 Selection of Study Population

A maximum accrual of 120 subjects in Phase 1 and Phase 2 portions of the study is expected at approximately 60 sites (20 sites for the Phase 1 portion and an additional 40 sites for the Phase 2 portion).

Phase 1: 4 to 48 evaluable subjects. In the event that each of the Dose Levels -1, 1, 2, and 3 is expanded to 12 subjects, a maximum of 54 subjects (allowing for 20% to be non-evaluable and including the additional 6 subjects for PK analysis) will be enrolled.

Phase 2 Cohorts 1 to 3: 10 to 20 evaluable subjects per cohort (maximum 22 subjects per cohort allowing for 10% to be non-evaluable). A maximum of 66 subjects will be enrolled in Phase 2. In each cohort, at least 50% of the subjects enrolled will be <18 years old at the time of informed consent.

Subjects who do not meet all of the inclusion criteria or who meet any of the exclusion criteria will not be eligible to receive study treatment.

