4 DETERMINATION OF SAMPLE SIZE

Phase 1 – Determination of the Maximum Tolerated Dose: The total number of subjects required for the Phase 1 portion of this study will depend upon the toxicities observed as the study progresses. The minimum number of evaluable subjects required for this study is 4. The projected maximum number of evaluable subjects required is 48. Once the MTD or RP2D has been defined, up to 6 additional subjects with recurrent or refractory solid tumors may be enrolled at the RP2D to acquire PK data in a representative number of young subjects. Therefore, a maximum of 54 subjects are expected to be enrolled in the 4 dose escalation levels, and PK expansion. The Phase 1 part of the study is expected to be completed within 18 months. In the event that each of Dose Levels -1, 1, 2, and 3 are expanded to 12 subjects, an absolute maximum of 54 subjects would be required allowing for 20% to be nonevaluable and including up to 6 additional subjects for PK analysis.

Phase 2: Phase 2 will require a minimum of 10 evaluable subjects per disease cohort and a maximum of 20 (10 evaluable subjects in each stage of Simon's optimal 2-stage design). Therefore, a maximum of 22 subjects per cohort will be enrolled to allow for a 10% nonevaluable rate. This design has 88% power to detect a 20% increase in the response rate

at the significance level of one-sided $\alpha = 0.07$ assuming a null response rate of 5% and alternative response rate $\geq 25\%$.

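### The Phase 1 maximum of 54 is said to allow for 20% non-evaluable subjects, but it equals 48 evaluable plus 6 PK subjects and contains no allowance

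*Protocol*

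**What the plan says.** Protocol Section 9.7.2 reaches the Phase 1 maximum twice in one paragraph.

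- First derivation: "The projected maximum number of evaluable subjects required is 48"; up to 6 further subjects may be added for PK once the MTD or RP2D is known; "Therefore, a maximum of 54 subjects are expected to be enrolled in the 4 dose escalation levels, and PK expansion".
- Second description: if all four dose levels are expanded to 12, "an absolute maximum of 54 subjects would be required allowing for 20% to be non-evaluable", with the up to 6 PK subjects included in that total.

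The Sample Size Rationale in the synopsis has the same paragraph. Under Number of Subjects, the synopsis takes the case in which all four levels "are expanded to 12 subjects and 6 additional subjects need to be enrolled in the PK Cohort, a maximum of 54 subjects" and attaches the same 20% remark. Protocol Section 9.3 has "a maximum of 54 subjects (allowing for 20% to be non-evaluable and including the additional 6 subjects for PK analysis) will be enrolled". SAP Section 4 carries it forward: "an absolute maximum of 54 subjects would be required allowing for 20% to be nonevaluable".

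The Phase 1 figure feeds the overall ceiling in Section 9.3: "A maximum accrual of 120 subjects in Phase 1 and Phase 2 portions of the study is expected".

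**The concern.** The same number is given two incompatible meanings. In the first derivation all 54 places are taken: 48 by evaluable subjects and 6 by PK subjects. In the second, some of the 54 are supposed to be a reserve for subjects who turn out not to be evaluable. Both cannot be true.

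The reserve matters because non-evaluable subjects add to enrolment. Protocol Section 9.1 says that subjects who leave in Cycle 1 for reasons other than a DLT, without having received 75% of the prescribed dose, are replaced. An ethics committee or regulator reading the sample-size section is told that the Phase 1 ceiling in children has a margin that it does not have. The overall maximum of 120 inherits the problem.

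**Working it through.** **Inputs**

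| Quantity | Value | Source |
|---|---|---|
| Dose levels × subjects per expanded level | 4 × 12 | Protocol 9.7.2 |
| Maximum evaluable, Phase 1 | 48 | Protocol 9.7.2, 9.3; SAP 4 |
| Additional PK subjects | up to 6 | Protocol 9.7.2; SAP 4 |
| Stated non-evaluable share | 20% | Protocol 9.7.2, 9.3; SAP 4 |
| Stated Phase 1 maximum | 54 | Protocol 9.7.2, 9.3; SAP 4 |
| Phase 2 maximum per cohort | 22 (20 evaluable, 10% non-evaluable) | Protocol 9.7.2 |
| Trial maximum | 120 | Protocol 9.3 |

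**Step 1: reproduce the stated figures.** 4 × 12 = 48, and 48 + 6 = 54. For the trial, 3 × 22 = 66 and 54 + 66 = 120. Both totals are reproduced with a Phase 1 allowance of zero.

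**Step 2: apply the stated 20%.** Let n be the evaluable target and d the non-evaluable share.

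| Convention | Calculation | Phase 1 maximum |
|---|---|---|
| n/(1 − d), plus PK | 48/0.8 = 60; 60 + 6 | 66 |
| n × (1 + d), plus PK | 48 × 1.2 = 57.6, rounded up to 58; 58 + 6 | 64 |
| Inflated per level, plus PK | 12/0.8 = 15, and 12 × 1.2 = 14.4, rounded up to 15; 4 × 15 + 6 | 66 |
| PK subjects inflated too, n/(1 − d) | 54/0.8 = 67.5, rounded up | 68 |
| PK subjects inflated too, n × (1 + d) | 54 × 1.2 = 64.8, rounded up | 65 |

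The range is 64 to 68. None of these gives 54.

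**Step 3: try reading the 48 as enrolled subjects.** Then 48 × 0.8 = 38.4, so about 38 would be evaluable. That contradicts the documents, which call the 48 evaluable.

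**Step 4: compare with Phase 2.** There the allowance is added: 20 × 1.10 = 22. So the 120 combines a Phase 2 part that contains its stated allowance with a Phase 1 part that does not. With Phase 1 corrected, the trial maximum is 66 + 66 = 132, or 64 + 66 = 130.

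**Step 5: find how far 54 does stretch.** With 6 places for PK, 48 remain for dose escalation.

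- At 20% of those enrolled, 48 × 0.8 = 38.4, so 38 evaluable subjects are covered.
- Three levels of 12: 36/0.8 + 6 = 51, which fits.
- 39 evaluable: 39/0.8 = 48.75, rounded up to 49; 49 + 6 = 55, which does not fit.
- Under n × 1.2 the limit is a little later: 40 × 1.2 + 6 = 54 fits; 41 × 1.2 = 49.2, rounded up to 50, + 6 = 56 does not.

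**The case against.** No reading rescues the 20% remark, so the case on the other side concerns size and remedy.

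- **The worst case is remote.** Expansion is only an option ("expansion of the cohort to 12 subjects will be considered"). It needs two DLTs of different classes, one apparently unrelated to dose, ready reversibility, and agreement of the steering committee and the sponsor. Dose Level -1 opens only if the MTD is exceeded at Level 1. For all four levels to fill, Levels 1 and 2 must be left upward with fewer than 6 subjects and re-entered on the way down. The PK addition is also 0 to 6, not always 6. This stands, and it limits the practical harm. It does not correct the sentence, because full expansion of all four levels is the scenario the documents chose to justify 54.
- **The protocol's own convention looks like n × (1 + d).** The Phase 2 figure of 22 is 20 × 1.10, whereas 20/0.9 = 22.2 would round up to 23. On that basis 64 and 130 are the closer counterparts, and the break point is 40/41 instead of 38/39. This is a fair qualification. However, multiplying by 1.2 makes the non-evaluable share 0.2/1.2, about 16.7% of those enrolled. A literal 20% of enrolled subjects gives 66, 132 and 38/39.
- **Deleting the clause leaves no room for replacements in the worst case.** This is true and should be acknowledged. The ceiling never had that room; deletion makes the text say so.
- **Phase 1 may already be closed.** On the plan's timetable (start in April 2017, Phase 1 within 18 months), Phase 1 accrual would precede the SAP of September 2022. The documents do not report actual status, so this is an inference. If it is right, raising the ceiling is moot and only the wording correction remains.

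**Conclusion.** The concern holds. The 54 has a zero allowance for non-evaluable subjects, and the statement that it allows for 20% is wrong in five places across the protocol and SAP. In the scenario the documents describe, the shortfall is 12 subjects (66 against 54) at 20% of those enrolled, or 10 (64 against 54) under n × 1.2. These figures assume that all 6 PK places are used and that the PK subjects themselves are not inflated.

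This is a definite error with limited consequences. It should be corrected, but no escalation decision, Phase 2 significance level or power figure depends on it.

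**What to change.** **Preferred.** Keep 54 and 120, and delete the clause about 20% being non-evaluable in:

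- the Protocol synopsis, under Number of Subjects and under Sample Size Rationale;
- Protocol Section 9.3;
- Protocol Section 9.7.2;
- SAP Section 4.

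A short added statement that 54 contains no margin for replacing non-evaluable subjects would make the ceiling fully transparent. This is a wording change with no effect on enrolment.

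**Alternative, if the allowance is really intended.** In the same places, and wherever the trial maximum of 120 appears (synopsis and Protocol Section 9.3), restate the maxima as 66 for Phase 1 and 132 for the trial. Use 64 and 130 only if the n × 1.2 convention is stated. This raises the paediatric enrolment ceiling and needs a protocol amendment.

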9.7.3 Interim Analysis

For each disease cohort (Ewing sarcoma/pPNET, rhabdomyosarcoma and HGG) in Phase 2, there will be 1 futility analysis: this is planned for after the first 10 evaluable subjects have completed at least 4 treatment cycles and, if applicable, a confirmatory scan has been performed (in case of a PR or CR at week 16), or have discontinued study drug early (before Week 16). At the futility analysis, if there are no responders (CR/PR), then the enrollment for that cohort will be discontinued for lack of efficacy. If 1 or more responses are observed, the accrual will continue.

Independent data monitoring committee (IDMC)

Safety monitoring will be conducted by an independent data monitoring committee (IDMC). The frequency of safety reviews will be defined in the IDMC charter. Minutes from the open meetings of the IDMC will be provided if requested by regulatory agencies. The function and membership of the IDMC will be described in the IDMC charter.

